### Screening Procedures:

At Screening the PI and the co-investigators will conduct a review of inclusion/exclusion criteria to determine the subject's eligibility for enrollment. Study procedures will be reviewed with the subject, and documentation of informed consent will be obtained.

### **At Visit 1 the following procedures will be completed:**

- Discuss study-specific procedures with the subject;
- Review inclusion and exclusion criteria, including list of current medications;
- Obtain a signed and dated consent form;
- Demographic Data;
- Review the subject medical history with the study coordinator.

STU#:

- Measure blood pressure, heart rate and respiratory rates will be measured.
- Measure height and weight
- Urine sample for illicit drugs test and pregnancy exam (if applicable);
- Fill out a screening form to make sure it is safe for the subject to have a brain scan and stimulation sessions. It is important that the subjects inform the study coordinator if they have any history of:
  - Metal fragments in their eyes or face.
  - Implantation of any electronic devices such as (but not limited to) cardiac pacemakers, cardiac defibrillators, cochlea implants or nerve stimulators.
  - Surgery on the blood vessels of their brain or the valves of the heart
  - Claustrophobia (fear of enclosed places)
  - Body piercing or tattoos
- Smartphone pain app rating\*;
- A 15-minute MRI scan;
- Personal Health History (PHH)
- Complete questionnaires about general health and pain
  - Safety questionnaires for the TMS procedures.
  - PainDetect;
  - Short-form Montreal Pain Questionnaires (sfMPQ);
  - BDI
  - Pain Catastrophizing scale
  - PROMIS 57

\* PainApp: participants will be instructed to use our smartphone-based app to report pain intensity (NRS, where 0 is no pain and 10 is worst imaginable pain), mobility (minimum, average, maximum), mood (NRS, where -10 is sad and +10 is happy), and medication use, collected twice daily from Visit 1 until the end of participation (~100 ratings).

### **MRI Scan:**

Subjects will undergo MRI scanning at the Northwestern University, Department of Radiology Center for Translational Imaging (CTI). All procedures are standard in our laboratory and have been approved in multiple previous IRB protocols.

More specifically, we will conduct a MRI scan (Siemens Trio, 3T, 64-channel head coil) with both structural (T1 scan, 5 minutes) and rsfMRI (EPI scan, 8 minutes) protocols. No contrast will be used in the MRI.

The structural scan will allow us to use the built-in neuronavigation TMS system, for optimal localization of the stimulation sites. Resting-state fMRI will be used to identify the functional localization for indirect stimulation of the hippocampus. To do so, we will follow a well-established in-house processing pipeline, replicating the methods used in our previous experiments using this method . Briefly, whole-brain seed-based correlation will be performed, using the left dorsal hippocampus as a seed region. This will allow us to identify, at a single-subject level, the exact parietal target that has maximal connectivity to the dorsal hippocampus. By stimulating this parietal target, modulation of the hippocampus connectivity can be achieved non-invasively  and with long-lasting effects in brain connectivity after three stimulation sessions .

In this same visit, participants will further complete questionnaires regarding pain ratings and the characteristics of their pain (see below for detail information).

Participants will be assigned to one of the six possible stimulation sequences and trained on our pain app (a smartphone-based tool used to rate pain and mood on NRS scales, as well as indicate rescue medication use, twice a day). They will be asked to use the pain app for the next 7-10 days prior to the first round of intervention and during all the study duration.

STU#:

There will be 2 MRI visits: one at baseline (visit 1), the second MRI will depend on participants allocation: participants randomized to group 1 will have a second MRI at visit 6; and participants randomized to group 2 at visit 11.

- **Visit 2 – 11** (Approx Time: 1 hour)

Intervention visits: These visits will be scheduled ~1 week after the visit 1 measurements are done.

At visit 2, the stimulation protocol will start, and participants will receive a total of 10 sessions: 5 consecutive daily sessions of each stimulation round following the prior stimulation sequence order, interleaved by 2 weeks of wash out period. All subjects will undergo sessions of sham, and hippocampal-stimulation, in a crossover manner. As different stimulation conditions (hippocampal, M1 or sham) will be delivered in each of the two rounds of stimulation, participants will be told that stimulations can feel and sound different.

Before stimulation, the subjects will complete the following assessments:

- NRS for back pain

After each session, subjects will complete the following assessments:

- Side Effects Questionnaire for rTMS
- NRS for back pain
- At visits 6 and 11 participants will also complete the following questionnaires:
  - PainDetect;
  - Short-form Montreal Pain Questionnaires (sfMPQ);
  - BDI

Global impression of changeAfter the end of Round 1 or Round 2:

- MRI

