## **STUDY INTERVENTION(S) / INVESTIGATIONAL AGENT(S):**

### **Brain Stimulation**

For the brain stimulation we will use Repetitive Transcranial Magnetic stimulation (rTMS). The sessions will be performed at either the CTI or the LHN. Repetitive TMS parameters are determined based on the allowable dosage of rTMS delivery, calculated based on published standards for experimental rTMS protocols, and in accordance with standard operating procedures for rTMS. Previous studies have shown that four or more rTMS sessions are needed to induce changes in the hippocampal network connectivity.

The brain stimulation can be delivery using different devices; in this project we will use a MagPro X100 stimulator connected to a MagPro Cool-B65 liquid-cooled butterfly coil (MagVenture A/S, Farum, Denmark). Resting motor threshold (M1-rTMS) will be determined during the visit 1 or visit 2 and used along the 10 visits. Single TMS pulses are delivered to the thumb-control area of the brain's primary motor cortex and the pulse intensity required to reliably evoke movement of the thumb is determined. This value is used as each individual subject's “motor threshold”, and stimulation is delivered at a proportion of the motor threshold.

STU#:

The rTMS pulse sequences and intensities used are all within the published safety guidelines.

As different stimulation conditions (hippocampal, M1 or sham) will be delivered in each of the three rounds of stimulation, participants will be told that stimulations can feel and sound different. All participants will receive all the 3 modalities of stimulation following specific order (see details below).

- **Stimulation Modality 1- Hippocampus-stimulation:**

Repetitive TMS will be applied at 100% resting motor threshold intensity to a region of interest located in the parietal cortex, that will be determined based on its connectivity with the hippocampus. This stimulation consists of a series of 1,600 pulses administered as 2-second periods of 20 Hz pulse trains separated by 28-s inter-train intervals (~20 minutes for the entire daily stimulation session). The induced current field will be oriented perpendicular/anterior to the long axis of the gyrus encompassing the stimulation location.

- **Stimulation Modality 2-Sham-stimulation:**

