#### **Stimulation modality sequences:**

The order of the stimulation modalities will be different across subjects. Subjects will be randomly assigned to one of two possible groups/stimulation sequences (fig 1). Before enrollment starts, we will produce 18 envelopes containing the stimulation sequence (see below possible combinations; we expect to use only 16). The stimulation sequence will be kept in sealed envelopes; therefore, subjects will get their assignment according to the order of entrance in the study. The study coordinator will retain the original sequence list which will be kept in a locked place. The study staff who provides the stimulation TMS session will be the only un-ed personnel.

STU#:

[figure not shown]

Figure 1: Study design and stimulation sequence. The subjects will be allocated to 1 envelop according to the entrance in the study. All participants will receive all the 2modalities of stimulation. Each round is composed by 5 daily session of stimulation, participants will not know which round is active and which is sham. Participants randomized to group 1 will have a second MRI at visit 6; and participants randomized to group 2 at visit 11.

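### The protocol gives two stimulation sequences in one section and six in another, keeps an M1 condition it does not define, and does not say how the envelope list is generated

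*Combined protocol and SAP*

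**What the plan says.** The section Stimulation modality sequences sets the allocation: "Subjects will be randomly assigned to one of two possible groups/stimulation sequences". The Figure 1 legend in that section gives two modalities, five daily sessions per round, and a second MRI at visit 6 for group 1 and at visit 11 for group 2. On the list, the section says "we will produce 18 envelopes containing the stimulation sequence (see below possible combinations; we expect to use only 16", and envelopes are used in order of entry. It gives no ratio, block size or method of generating the list. Figure 1 itself was not available for this review.

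Other sections describe something else:

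- MRI Scan (Visit 1): "Participants will be assigned to one of the six possible stimulation sequences and trained on our pain app". The same section later times the second MRI by group 1 or group 2.
- Brain Stimulation: "As different stimulation conditions (hippocampal, M1 or sham) will be delivered in each of the three rounds of stimulation", and "All participants will receive all the 3 modalities of stimulation following specific order". Only a hippocampal and a sham modality are then described.
- Visits 2–11: ten sessions, with sham and hippocampal stimulation in a crossover, but the next sentence has "different stimulation conditions (hippocampal, M1 or sham) will be delivered in each of the two rounds of stimulation".

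Both sentences that name M1 give the mix of conditions as the reason for warning participants that rounds may differ in sensation and noise.

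The Data Analysis Plan names hippocampal and sham stimulation as the only factors in a within-subject ANOVA. The Power Calculation aims for 12 participants and recruits 16. Under Withdrawal of Participants, incomplete data sets are left out of the primary analysis.

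**The concern.** Whoever fills the envelopes needs one set of sequences, and the protocol supplies two. Table 1 schedules randomisation at Visit 1, and it is the Visit 1 text that says six. An envelope made from that wording would call for M1 stimulation, for which no intensity or pulse train is given as a treatment. If the six sequences were used, four would have no second MRI visit, although connectivity change is the main study aim.

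The second issue is balance. In a two-period crossover, equal numbers in the two orders cancel any period difference out of the treatment contrast. With unequal numbers and no period term, part of it stays in. The Data Analysis Plan would call the approach clinically important on the strength of this contrast, and with 12 to 16 participants a difference of two or four between the orders is not negligible.

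**Working it through.** **Plan's own figures.** The protocol gives no dropout rate. From 12 completers and 16 recruited, the implied loss is 1 − 12/16 = 25%, and 12/(1 − 0.25) = 16. This is back-solved, so it is not an independent check. The 18 envelopes equal 2 × 9 and also 6 × 3, so that count does not tell the two designs apart.

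**Number of orders.** With k conditions, each given once, there are k! orders: 2! = 2 and 3! = 6. Two sequences and six sequences therefore describe different trials.

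**Which design the rest of the protocol fits.** With five sessions per round, two rounds give 2 × 5 = 10 sessions, and Visit 1 makes 11 visits. Three rounds would give 3 × 5 = 15 sessions and 16 visits. Study Timelines has 11 visits, and the Visits 2–11 text and the compensation table have 10 sessions. M1 otherwise appears only in setting the motor threshold.

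**Split between the two orders.** Assumptions: the 18 envelopes are 9:9 in random order, and loss to 12 completers is unrelated to sequence.

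- At 16 used, the split is 8:8 only if the two unused envelopes are one of each kind: 9 × 9 / C(18,2) = 81/153 = 0.529. Otherwise it is 9:7, with probability 0.471. Nothing worse is possible.
- At 12 completers, P(8:4 or worse) = 2 × [C(9,8) × C(9,4) + C(9,9) × C(9,3)] / C(18,12) = 2 × (9 × 126 + 84) / 18,564 = 2,436/18,564 = 0.131.
- At 12 completers drawn from an 8:8 allocation, P(8:4) = 2 × C(8,8) × C(8,4) / C(16,12) = 140/1,820 = 0.077, and nothing worse is possible.
- If each envelope were instead drawn independently with probability one half (the other assumption that the silence allows), P(8:4 or worse) at 12 is 0.388, and P(10:6 or worse) at 16 is 0.454.

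**Effect on the contrast.** Write τ for the treatment effect and π for the period difference, with no carryover. The within-person difference is τ + π in one order and τ − π in the other, so its mean over n1 and n2 participants is τ + π × (n1 − n2)/(n1 + n2).

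| Split | Share of π in the contrast |
|---|---|
| 9:7 | 2/16 = 0.125 |
| 7:5 | 2/12 = 0.167 |
| 8:4 | 4/12 = 0.333 |

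The documents give no value for π. For an assumed 1 point on the 0–10 scale, the shift is 0.125 points at 9:7 and 0.33 points at 8:4, in proportion for other values.

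**The case against.** The best reply is that the intended design can be recovered. The allocation section itself says two sequences, only two modalities are described and analysed, the visit and session counts fit two rounds, and the six-sequence phrase sits in a sentence that also covers pain-app training. This stands, and it shows which way to reconcile the text. It does not remove the conflict: the other statements are current text, and one of them describes assignment at Visit 1.

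On balance, the reply is that the documents are silent rather than wrong. A 9:9 list could do no worse than 9:7 at 16. Chance imbalance has random sign, so it adds noise rather than a predictable bias. Blocking only lowers 13.1% to 7.7% among completers. All of this is correct, so balance is the secondary point.

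A reader might also infer four stronger things that the documents do not support:

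- That the list is unblocked. No method is stated either way, and Figure 1 might show more about the sequences.
- That 18 envelopes prove a six-sequence list. The count fits both designs.
- That only 6 of 18 envelopes would contain both conditions. This needs three-condition orders cut to their first two rounds, which is nowhere described. If M1 were struck out instead, the six orders would become three hippocampal-first and three sham-first, and 18 envelopes would be exactly 9:9.
- That the warning about differing sensations reveals sham. It does not say which round is sham, and the sham procedure includes a skin electrode meant to mimic the real sensation.

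**Conclusion.** The allocation instructions contradict each other on the number of sequences (two or six), conditions (two, or three with M1) and rounds (two or three). This rests on the wording alone and needs no assumption. It should be corrected before envelopes are made, because M1 is undefined as a treatment and the MRI timing and the analysis cover only the two-condition design.

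Balance between the two orders is not assured, which is weaker than saying that it fails. Under a 9:9 list and dropout unrelated to sequence, the chance of 9:7 at 16 is 47%, and of 8:4 or worse at 12 is 13%. Without a period term, between one eighth (9:7) and one third (8:4) of any period difference then enters the contrast, in a direction set by chance. The size of the period difference is unknown.

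**What to change.** Reconcile the Brain Stimulation, MRI Scan and Visits 2–11 text with the two-sequence, two-round crossover that the allocation section, the ten sessions and the Data Analysis Plan support. The M1, three-modality, three-round and six-sequence statements are the ones that conflict with it. In the same edit, revise the stated reason for the warning to participants, and use one neutral wording for both rounds.

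Specify a 1:1 envelope list in permuted blocks, for example four blocks of four, so that the first 16 split 8:8. State how the list is generated. If spare envelopes are wanted, add a further complete block.

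Blocking governs the split at entry only. If the sponsor also wants protection after dropout, a period term in the ANOVA would remove the remaining share. At 8:4 its efficiency relative to an even split is 4 × 8 × 4/12² = 0.889.

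The cost is protocol wording and a new envelope list before enrolment, with no extra participants or visits.

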Demographic survey and patient information criteria	X		
Pregnancy test (if applicable) 	X	X 	
Drug urine test	X		
Vitals measurements	X		
Personal Health History (PHH)	X		
General physical exam	X		
BDI	X		
MRI	X		X 
Pain Detect Questionnaire (Pdq)	X		X
Short-form Montreal Pain Questionnaires (sfMPQ)	X		X
Pain Catastrophizing Scale (PCS)	X		
NIH PROMIS-57 Profile	X		
Randomization	X		
rTMS stimulation		X	X
NRS before/after stimulation		X	X
NRS average pain			X
Adverse events questionnaire		X	X
PainApp (During all the study) 	X	X	X
Approximate visit duration	2-3 hrs	1-2 hrs	1-2 hrs

**Table 1:** Related Procedures and Study Schema. Visits 1 through 10 will be completed according to the presented schema. 1. There is no specific recommendation for or against pregnancy, however, since this study will be utilizing Repetitive TMS as a mode of intervention, we will take the conservative approach and exclude pregnancy. Female subjects of childbearing potential will be asked to take a pregnancy test. If the pregnancy test is positive, the subject may not enroll in the study. Pregnancy test will be repeated in visits 2 and 8 (every ~ 2 weeks).

STU#:

2. Visit 6 and 11: These visits will be separated in two parts: part 1: last day of stimulation (stimulation + questionnaires) and part 2: MRI (at least 24hrs after part 1). For group 1, only visit 6 will have 2 parts and for group 2 only visit 11 (see Figure 1 for details).
3. PainApp: participants will be instructed to use our smartphone-based app to report pain intensity (NRS, where 0 is no pain and 10 is worst imaginable pain), mobility (minimum, average, maximum), mood (NRS, where -10 is sad and +10 is happy), and medication use, collected twice daily from Visit 1 until the end of participation).

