## WITHDRAWAL OF PARTICIPANTS

Participants may be withdrawn from the study if they are not able to undergo brain MR imaging or if they do not provide regular pain data with the cellphone app. Participants will be notified that they will have to discontinue the study if those circumstances occur.

If a participant withdraws early, payment will be made for the portion of the research study that has been completed (prorated to the nearest 1-hour increment). Incomplete data sets obtained from participants (due to early withdrawal) will be excluded from the primary analysis and included in an exploratory full dataset analysis.

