### **MR Imaging**

Individuals who cannot tolerate the confinement of an MRI scanner and those who may not be able to be scanned because of implanted metal devices will be excluded. Claustrophobia is the main limiting factor; we attempt to identify people at risk by having people lie in the simulation scanner (a fake scanner made to look and feel like the real one) to assess their comfort levels. There is a standard checklist of additional exclusionary items for MR scanning (e.g., implanted devices, exposure to metallic fragments at work, etc) that will be utilized prior to entering participants into the study and again prior to each imaging session. Personnel continuously query the subject in the scanner as to their overall well-being during scans and will discontinue the scan

STU#:

and relieve the subject from the discomfort at any time requested. It is possible that the anatomical scans may uncover a brain abnormality of which the participant was not aware. In such cases, the subject is removed from the study and given appropriate medical advice ([name]); his/her scans are sent to a radiologist for an opinion and this person then consults with [name]. The likelihood of this happening is low (less than 1%). Over the last 20 years of doing brain scans in various populations (healthy and not), participants often are surprised at how anxious they feel in the scanner and simply cannot tolerate it. Otherwise, subjects are usually enthusiastic in participating in trials that may lead to new discoveries that either pertain to their conditions or help other people.

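### The stimulation sequence is assigned at visit 1, before the diary period and the remaining pre-stimulation checks, so anyone lost before the first session becomes a post-randomisation exclusion

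*Combined protocol and SAP*

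**What the plan says.** In Table 1 the row "Randomization" is marked under visit 1 only. The MRI Scan section agrees, placing assignment in the same visit as app training: "Participants will be assigned to one of the six possible stimulation sequences and trained on our pain app". The diary period follows: "They will be asked to use the pain app for the next 7-10 days prior to the first round of intervention". On the stimulation visits the section says "These visits will be scheduled ~1 week after the visit 1 measurements are done".

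Under Stimulation modality sequences there are two sequences, 18 sealed envelopes are prepared with 16 expected to be used, and "subjects will get their assignment according to the order of entrance in the study". The coordinator keeps the sequence list in a locked place. No allocation ratio or blocking is stated.

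Under Withdrawal of Participants, people may be withdrawn if they cannot undergo MRI or "if they do not provide regular pain data with the cellphone app". The consequence is that "Incomplete data sets obtained from participants (due to early withdrawal) will be excluded from the primary analysis"; such data go only into an exploratory analysis. For an unexpected brain abnormality, the MR Imaging section says "In such cases, the subject is removed from the study and given appropriate medical advice".

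The Data Analysis Plan compares hippocampal and sham stimulation by within-subject ANOVA and names no period or sequence factor.

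**The concern.** Nothing done to the participant between visits 1 and 2 depends on the sequence. Assigning it at visit 1 therefore turns what could be recorded as a pre-randomisation loss into a post-randomisation exclusion. Three things are at stake:

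- **Participant flow.** Each such loss uses an envelope. The plan has no rule for reusing an opened envelope or replacing the participant.
- **Sequence balance.** A crossover analysed without a period term relies on equal sequence numbers to cancel any difference between round 1 and round 2.
- **Withdrawal decisions.** The app-data rule is discretionary. Risks to Participants says only subjects are blinded, while Stimulation modality sequences gives the list to the coordinator and appears to limit unblinding to the staff who stimulate. On either text, someone deciding a withdrawal before visit 2 could know that participant's sequence.

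**Working it through.** **1. What can remove a participant between assignment and the first session**

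- Irregular app data (Withdrawal of Participants): discretionary and study-wide, with no threshold and no stated pre-stimulation cut-off.
- Incidental brain finding (MR Imaging): stated likelihood below 1%. At that bound the expected number in 16 is 16 × 0.01 = 0.16, and the chance of at least one is 1 − 0.99^16 = 0.15.
- Repeat pregnancy test at visit 2 (Table 1, note 1). That note and the exclusion criteria conflict with the last sentence of Risks to Participants on whether pregnancy excludes; these must be reconciled.
- Motor threshold, set at visit 1 or visit 2 (Brain Stimulation): relevant only if left to visit 2. No section names a failed threshold as a ground for removal.

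The plan gives no rate for diary failure or ordinary drop-out in this interval.

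**2. The plan's own numbers**

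The Power Calculation section recruits 16 to finish with 12. The implied loss is 4/16 = 25%, and 12/(1 − 0.25) = 16. This is only a consistency check, since the plan states no dropout rate.

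**3. Effect of losses on balance**

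Assume 8:8 allocation and losses at random. The chance that *a* of *k* losses fall in sequence 1 is C(8,a) × C(8,k−a) / C(16,k).

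- k = 1: always 8:7.
- k = 2: 7:7 has 64/120 = 0.53; 8:6 in either direction has 56/120 = 0.47.
- k = 4 (the whole allowance): 6:6 has 784/1820 = 0.43; 7:5 in either direction has 896/1820 = 0.49; 8:4 in either direction has 140/1820 = 0.08.

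The k = 4 case includes later dropouts. Moving randomisation prevents only the imbalance that arises before visit 2.

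**4. What imbalance does without a period term**

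Let τ be the active-minus-sham effect and π the round 1 minus round 2 difference. People given active first contribute τ + π on average; people given sham first contribute τ − π. The overall mean is τ + π(n1 − n2)/N. The share of π carried into the treatment estimate is therefore:

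- 8:7: 1/15
- 8:6: 2/14 = 1/7
- 7:5: 2/12 = 1/6
- 8:4: 4/12 = 1/3

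At 7:5, each point of period difference on the 0–10 scale shifts the estimate by about 0.17 points. The plan gives no value for π.

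**5. Number of completers**

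With k losses before visit 2 and 16 consented, 16 − k people start stimulation whichever visit the envelope is opened at. Participant Population(s) sets the maximum consented at 16, so timing alone recovers nobody.

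**The case against.** Much of the case on the other side stands.

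- **Bias.** A person never stimulated could not enter a within-subject comparison under any rule. Participants are blinded, so their own decision to leave before the first session cannot depend on sequence. Only the route through staff discretion remains.
- **Scan losses.** A reader might infer that assignment precedes the reading of the scan. No section says when the scan is read or the target processed. A reader might also count people who cannot tolerate the baseline scan as post-assignment losses. The MRI Scan section describes the scan first and assignment afterwards; MRI contraindication is an exclusion criterion, and a simulation scanner is used to find people at risk. The documents support neither reading.
- **Numbers.** A reader might infer that early randomisation uses up the four-person dropout allowance. Early losses do use it, but they would under any timing. For illustration, assume 12.5% lost before stimulation and 20% of the rest later. The chance that at least 12 of 16 finish is the binomial tail at 0.875 × 0.80 = 0.70, which is 0.45. It rises to 0.80 if 16 are randomised after the early losses, but that needs about 16/0.875 = 18.3, so 19 consents. That gain comes from raising the cap.
- **Balance.** The ratio is unstated, two spare envelopes exist, and later dropout can unbalance the sequences anyway. The precision cost is small: a 7:5 split keeps 4 × 7 × 5/144 = 97% of the efficiency of 6:6. The objection does not remove the shift in step 4, which is an offset and not a loss of precision.
- **Diary.** App use before round 1 is not described as an eligibility gate, so a fix should not assume a compliance threshold.
- **Logistics.** Group 1's second MRI depends on the assignment, and the scanners are shared, so late assignment has a booking cost.

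**Conclusion.** The point holds in a limited form. Assignment at visit 1 precedes the diary period and any checks left to visit 2, and the withdrawal rule makes losses in that interval post-randomisation exclusions. The consequences are an untidy participant flow, avoidable sequence imbalance in a model with no period term, and discretionary withdrawals that staff may make knowing the sequence.

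The size is modest. One pre-stimulation loss from 8:8 carries 1/15 of any period difference into the treatment estimate, and two carry either nothing or 1/7. If all four allowed losses occur over the study, exact balance survives with probability 0.43. These figures assume 8:8 allocation and random loss; the number lost before visit 2 and the size of any period difference are unknown. The finding does not show that the pain comparison would be materially biased. For a 16-person pilot, this is a worthwhile and inexpensive correction.

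**What to change.** Make four linked edits:

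1. In Table 1, move the randomisation mark from visit 1 to visit 2.
2. In the MRI Scan section, replace the assignment sentence with wording such as: the next envelope is opened at visit 2, immediately before the first session, once the existing pre-stimulation checks are complete. Reconcile its six sequences with the two under Stimulation modality sequences.
3. Under Stimulation modality sequences, tie envelope order to reaching the first session and not to study entry. Otherwise the sequence is still fixed at entry, whenever the envelope is opened.
4. State that whoever decides a pre-stimulation withdrawal does not hold the sequence list, and that losses before opening are reported as pre-randomisation losses.

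The cost is in scheduling. Group 1's second MRI comes at least 24 hours after the fifth daily session, so it must be booked at about a week's notice (five days at the least), or slots held provisionally for both groups. No new eligibility criterion is needed.

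A period term in the ANOVA would complement this by also dealing with imbalance from later dropout. It costs one error degree of freedom (10 instead of 11 with 12 completers). If the aim is also to make 12 completers more likely, the 16-person consent cap must be raised as a separate change.
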